## Appendix I Abbreviations

| Abbreviation or special term | Explanation   |
|------------------------------|---|
| ACC/AHA                      | American College of Cardiology/American Heart Association   |
| AE                           | Adverse Event   |
| ADA                          | Anti-drug antibody  |
| ALP                          | Alkaline Phosphatase  |
| ALT                          | Alkaline Aminotransferase   |
| Apo                          | Apolipoproteins   |
| aPTT                         | Activated Partial Thromboplastin Time   |
| ASO                          | Antisense Oligonucleotide   |
| AST                          | Aspartate Aminotransferase  |
| BMI                          | Body Mass Index   |
| BP                           | Blood Pressure  |
| bpm                          | Beats Per Minute  |
| BUN                          | Blood Urea Nitrogen   |
| CI                           | Confidence Interval   |
| CK                           | Creatine Kinase   |
| CRO                          | Contract Research Organisation  |
| CSA                          | Clinical Study Agreement  |
| CSP                          | Clinical Study Protocol   |
| CSR                          | Clinical Study Report   |
| CVD                          | Cardiovascular Disease  |
| DBP                          | Diastolic Blood Pressure  |
| DILI                         | Drug Induced Liver Injury   |
| EC                           | Ethics Committee, synonymous to Institutional Review Board (IRB) and Independent Ethics Committee (IEC) |
| ECG                          | Electrocardiogram   |
| eCRF                         | electronic Case Report Form   |
| EDC                          | Electronic Data Capture   |
| EDTA                         | Ethylenediaminetetraacetic Acid   |
| EDV                          | Early Discontinuation Visit   |
| eGFR                         | Estimated Glomerular Filtration Rate  |
| FDA                          | U.S. Food and Drug Administration   |
| FSH                          | Follicle-stimulating Hormone  |
| GCP                          | Good Clinical Practice  |
| GGT                          | Gamma Glutamyl Transpeptidase   |

| Abbreviation or special term | Explanation  |
|-------------------------------------|---|
| GLDH                                | Glutamate Dehydrogenase                                   |
| Hb                                  | Haemoglobin   |
| HbA1c                               | Haemoglobin A1c   |
| HCT                                 | Haematocrit   |
| HDL-C                               | High-density Lipoprotein Cholesterol                      |
| HIV                                 | Human Immunodeficiency Virus                              |
| HL                                  | Hy's Law  |
| HMG-CoA                             | 3-hydroxy-3-methyl-glutarylcoenzyme A                     |
| HR                                  | Heart Rate  |
| hs-CRP                              | High sensitive C-reactive Protein                         |
| IATA                                | International Airline Transportation Association          |
| IB                                  | Investigator's Brochure                                   |
| ICF                                 | Informed Consent Form                                     |
| ICH                                 | International Council for Harmonisation                   |
| IRB/IEC                             | Institutional Review Boards/Independent Ethics Committees |
| ISR                                 | Injection Site Reaction                                   |
| IUD                                 | Intrauterine Device                                       |
| LDL                                 | Low-density Lipoprotein Cholesterol                       |
| LDL-C                               | Low-density Lipoprotein Cholesterol                       |
| LH                                  | Luteinizing Hormone                                       |
| LLN                                 | Lower Limit of Normal                                     |
| Lp(a)                               | Lipoprotein(a)  |
| MCH                                 | Mean Corpuscular Haemoglobin                              |
| MCHC                                | Mean Corpuscular Haemoglobin Concentration                |
| MCV                                 | Mean Corpuscular Volume                                   |
| NHP                                 | Non-compliance Handling Plan                              |
| PCSK9                               | Proprotein Convertase Subtilisin/Kexin type-9             |
| PEF                                 | Peak Expiratory Flow                                      |
| PD                                  | Pharmacodynamic   |
| PHL                                 | Potential Hy's Law  |
| PI                                  | Principal Investigator                                    |
| PK                                  | Pharmacokinetic   |
| QTcF                                | Corrected QT Interval by Fredericia                       |
| RBC                                 | Red Blood Cell  |
| RTSM                                | Randomization and Trial Supply Management                 |

| Abbreviation or special term | Explanation                       |
|-------------------------------------|--|
| SAE                                 | Serious Adverse Event                    |
| SBP                                 | Systolic Blood Pressure                  |
| SC                                  | Subcutaneous(ly)                         |
| SD                                  | Standard Deviation                       |
| SEM                                 | Standard Error of the Mean               |
| SoA                                 | Schedule of Activities                   |
| TBL                                 | Total Bilirubin                          |
| TC                                  | Total cholesterol                        |
| UACR                                | Urine Albumin to Creatinine Ratio        |
| ULN                                 | Upper Limit of Normal                    |
| UPCR                                | Urine Protein to Creatinine Ratio        |
| VLDL-C                              | Very-low-density lipoprotein cholesterol |
| WBC                                 | White Blood Cell                         |

---

## LIST OF ABBREVIATIONS

Abbreviation or special term	Explanation
ADA	Anti-drug antibody
AE	Adverse event
ALP	Alkaline phosphatase
ALT	Alanine aminotransferase
ANCOVA	Analysis of covariance
ApoA1	Apolipoprotein A1
ApoB	Apolipoprotein B
AST	Aspartate aminotransferase
ATC	Anatomical therapeutic chemical
BMI	Body mass index
CI	Confidence interval
CS	Compound symmetry covariance structures
CSP	Clinical study protocol
CSR	Clinical study report
CTMS	Clinical trial management system
CV	Coefficient of variation
D	Day
dLDL-C	Direct low-density lipoprotein cholesterol
ECG	Electrocardiogram
eCRF	Electronic case report form
EDV	Early discontinuation visit
EXP	Exponent
GGT	Gamma glutamyl transferase
HbA1c	Haemoglobin A1c
HDL-C	High density lipoprotein cholesterol
HLT	High level term
HR	Heart rate
hs-CRP	High-sensitivity C-reactive protein
ICF	Informed consent form
IDRP	Integrated data review plan
IP	Investigational product
IPD	Important protocol deviation
IRT	Interactive Response Technology
LDL-C	Low density lipoprotein cholesterol
LLOQ	Lower limit of quantification
Lp(a)	Lipoprotein(a)
Lsmean	Least squared mean
MedDRA	Medical Dictionary for Regulatory Activities
MMRM	Mixed model repeated measures
NHP	Non-compliance handling plan

PCSK9	Proprotein convertase subtilisin/kexin type-9
PD	Pharmacodynamic
PK	Pharmacokinetic
PT	Preferred term
QRS	QRS wave
QT	QT wave
QTcF	Corrected QT Interval using Fridericia's Formula
REML	Restricted maximum likelihood
RR	Respiratory rate
RTSM	Randomization and trial supply management
SAE	Serious adverse event
SAP	Statistical analysis plan
SC	Subcutaneous
SD	Standard deviation
SDTM	Study data tabulation model
SE	Standard error
SI	International system of units
SMQ	Standardized MedDRA queries
SOC	System organ class
SP(POW)	Power spatial covariance structures
TBL	Total bilirubin
TC	Total cholesterol
TE-ADA	treatment emergent ADA
TEAE	Treatment emergent adverse event
ULN	Upper limit of normal
UNS	Unscheduled
URC	Unblinding review committee team
VLDL-C	Very-low-density lipoprotein cholesterol
WHO	World Health Organization
WHO-DD	WHO Drug Dictionary

## AMENDMENT HISTORY

Version number	Date	Brief description of change
V1.0	18/11/2020	N/A
V2.0	09/04/2021	Minor amendment: added the IPD list, not available at the time of V1.0; reviewed some sections about external data, not available at the time of V1.0; added correlation analysis on LDL-c and additional figures for ADA parameters as per sponsor late request. All the other minor changes are reported in section 8.1.2.
V3.0	22/06/2021	Minor amendment: added “+1” in the calculation of durations for ADA measurements
V4.0	10/08/2021	Minor amendment: Rephrased the description of ADA boxplots

# 1 STUDY DETAILS

## 1.1 Study objectives

Objectives	Endpoints
Primary	

 
To assess the effect of different doses of AZD8233 on LDL-C versus placebo
 
	
 
Absolute change from baseline in log-transformed LDL-C in plasma
 

Secondary	

 
To assess the effect of different doses of AZD8233 on PCSK9 versus placebo
 
	
 
Absolute change from baseline in log transformed PCSK9 in plasma
 

 
To assess the effect of different doses of AZD8233 on LDL-C versus placebo
 
	
 
Percentage change from baseline in levels of LDL-C in plasma
 

 
To assess the effect of AZD8233 on other lipid parameters versus placebo
 
	
 
Levels of other lipid parameters including:                             
 
- TC
 
- HDL-C
 
- Non-HDL-C
 
- VLDL-C
 
- ApoA1
 
- ApoB
 
- Lp(a)
 
- Triglycerides
 
- Remnants cholesterol
 
 
 

 
To evaluate the PK of AZD8233
 
	
 
Plasma parameters: population PK parameters to be reported in a separate report.
 

 
To evaluate the immunogenicity of AZD8233
 
	
 
Development of ADA and titre (if participants are ADA-positive) during treatment and follow-up
 

Safety	

 
To assess the safety and tolerability of AZD8233
 
	
 
Safety and tolerability will be evaluated in terms of AEs, vital signs, ECG, and clinical laboratory evaluations including platelet count
 

Tertiary/Exploratory	

 
To assess lipoprotein profile following SC administration of AZD8233
 
	
 
Lipoprotein profile, including particle size and number
 

Objectives	Endpoints

 
To collect and store blood (plasma) and urine samples for potential future exploratory research aimed at exploring biomarkers involved in PK, PD, safety (including anti-platelet antibodies) and tolerability related to AZD8233 treatment or cardiometabolic diseases
 
	
 
Results of potential future exploratory biomarker research may be reported outside this study's CSR
 

 
Optional: To collect and store DNA from blood samples according to each country's local and ethical procedures for future exploratory research into genes/genetic variation that may influence response to treatment.
 
	
 
Results of possible future genetic research may be reported outside this study's CSR.
 

Two analyses are planned for this study:

- A primary analysis after the treatment period,
- A complete analysis after the final follow-up (after final database lock).

[figure not shown]
The two analyses will have the same scope, except for lipoprotein profile which will be included only in the complete analysis, as described in sections 2, 3 and 4. With the aim to maintain the blinding the primary analysis will be performed by an independent unblinded team. The purpose of the primary analysis is to help inform further clinical development; no changes will be made to this study unless a safety signal is observed. This analysis will not have any impact on the overall type-1 error because no changes will be made to the trial based on the outcome of the analysis (all efficacy data is already collected at the point of the primary analysis, no changes to the efficacy model will be made). The primary analysis will be done when all patients still in study have completed the treatment period (visit 10). Additional details will be given in the primary analysis charter and the Unblinded Review Committee (URC) charters (i.e. data cut-off rules, data cleaning, nomination of the unblinded biometrics team and the URC and the operational procedures used to protect the blinding).

## 1.2 Study design

This is a randomized, parallel, double-blind, placebo-controlled, dose-ranging Phase 2b study in approximately 108 participants with dyslipidaemia. The study will be conducted in up to 25 sites in up to 4 countries.

The screening period starts up to 42 days before the randomization visit and ends on Day -1. Eligible participants will attend 7 visits during the treatment period and 7 additional visits during the safety follow up period. Eligible participants are randomized across four different treatment arms in a 1:1:1:1 ratio stratified by region (North America vs Europe) for a 12-week treatment period. The planned treatment arms are AZD8233 CCI SC, AZD8233 CCI SC, AZD8233 CCI SC, and Placebo SC on Days 1, 8, 29, and 57.

**Figure 1 Study Design**

Note: All visits include blood and urine sample collection as well as safety assessment.  
D = dosing day; R = randomization

Note: All visits include blood and urine sample collection as well as safety assessment, except for Visit 2, which includes only blood sample collection.

D = dosing day; R = randomization

Subjects who discontinue the treatment but not the study, should perform the EDV at the next scheduled visit and then go to the following scheduled visits exactly as subjects who are still on-treatment, for a total of 3 months.

The table below shows all procedures to be conducted at the scheduled visits.

**Table 1 Schedule of assessment**

	Screening		Treatment Period							EDV	Safety Follow-up period	Final Follow-up Visit
	1	2	3	4	5 a	6	7 a	8	9 a			
Visit Number	1	2	3	4	5 a	6	7 a	8	9 a		10, 11 a , 12, 13 a , 14, 15 a	16
Study Week			0	1	3	4	6	8	10		12, 14, 16, 18, 20, 22	24
Study Day	D-42 to D-1 	D-7 to D-1	D1	D8	D22	D29	D43	D57	D71		D85, D99, D113, D127, D141, D155	D169
Visit Window				± 1 days	± 2 days	± 2 days	± 2 days	± 2 days	± 2 days		± 2 days	± 2 days
Informed consent	X											
Optional Informed consent for future genetic research sample	X											
Verify eligibility criteria	X		X b									
Enrolment in RTSM	X											
Randomisation in RTSM			X									
Medical history	X											
Concomitant medication review	X	X	X	X	X	X	X	X	X	X	X	X
Demographics	X											
Height	X											

**Table 1 Schedule of assessment**

	Screening		Treatment Period							EDV	Safety Follow-up period	Final Follow-up Visit
	1	2	3	4	5 a	6	7 a	8	9 a			
Visit Number	1	2	3	4	5 a	6	7 a	8	9 a		10, 11 a , 12, 13 a , 14, 15 a	16
Study Week			0	1	3	4	6	8	10		12, 14, 16, 18, 20, 22	24
Study Day	D-42 to D-1 	D-7 to D-1	D1	D8	D22	D29	D43	D57	D71		D85, D99, D113, D127, D141, D155	D169
Visit Window				± 1 days	± 2 days	± 2 days	± 2 days	± 2 days	± 2 days		± 2 days	± 2 days
Body weight c	X		X		X		X			X	X	X
BMI	X									X		X
HbA1c	X											
Viral serology	X											
Pregnancy and reproductive status (females only, pre-dose)	X		X									
Study intervention administration (AZD8233/Placebo)			X	X		X		X				
Adverse event review	X (SAE only)	X (SAE only)	X	X	X	X	X	X	X	X	X	X
Injection site reactions d			X	X	X	X	X	X	X	X	X	X

**Table 1 Schedule of assessment**

	Screening		Treatment Period							EDV	Safety Follow-up period	Final Follow-up Visit
Visit Number	1	2	3	4	5 a	6	7 a	8	9 a		10, 11 a , 12, 13 a , 14, 15 a	16
Study Week			0	1	3	4	6	8	10		12, 14, 16, 18, 20, 22	24
Study Day	D-42 to D-1 i	D-7 to D-1	D1	D8	D22	D29	D43	D57	D71		D85, D99, D113, D127, D141, D155	D169
Visit Window				± 1 days	± 2 days	± 2 days	± 2 days	± 2 days	± 2 days		± 2 days	± 2 days
Complete physical examination	X		X							X		X
Abbreviated physical examination				X	X	X	X	X	X		X	
Vital signs (blood pressure, pulse and temperature) e	X		X	X	X	X	X	X	X	X	X	X
ECG e	X		X	X		X		X		X	X f	X
Serum chemistry	X		X	X	X	X	X	X	X	X	X	X
Hematology	X		X	X	X	X	X	X	X	X	X	X
Coagulation parameters g	X		X	X	X	X	X	X	X	X	X	X
hs-CRP	X		X					X		X	X	X

**Table 1 Schedule of assessment**

	Screening		Treatment Period							EDV	Safety Follow-up period	Final Follow-up Visit
	1	2	3	4	5 a	6	7 a	8	9 a			
Visit Number											10, 11 a , 12, 13 a , 14, 15 a	16
Study Week			0	1	3	4	6	8	10		12, 14, 16, 18, 20, 22	24
Study Day	D-42 to D-1 i	D-7 to D-1	D1	D8	D22	D29	D43	D57	D71		D85, D99, D113, D127, D141, D155	D169
Visit Window				± 1 days	± 2 days	± 2 days	± 2 days	± 2 days	± 2 days		± 2 days	± 2 days
Complement activation panel g			X	X		X		X				
Urinalysis	X		X	X	X	X	X	X	X	X	X	X
Urine renal safety biomarkers	X		X	X	X	X	X	X	X	X	X	X
LDL-C h		X	X	X	X	X	X	X	X	X	X	X
PCSK9 h		X	X	X	X	X	X	X	X	X	X	X
Triglycerides h		X	X	X	X	X	X	X	X	X	X	X
Other Lipid parameters h			X	X	X	X	X	X	X	X	X	X
Lipoprotein profile h			X	X	X	X	X	X	X	X	X	X
PK plasma sample i				X		X	X	X	X	X	X i	X

**Table 1 Schedule of assessment**

	Screening		Treatment Period							EDV	Safety Follow-up period	Final Follow-up Visit
	1	2	3	4	5 a	6	7 a	8	9 a			
Visit Number											10, 11 a , 12, 13 a , 14, 15 a	16
Study Week			0	1	3	4	6	8	10		12, 14, 16, 18, 20, 22	24
Study Day	D-42 to D-1 i	D-7 to D-1	D1	D8	D22	D29	D43	D57	D71		D85, D99, D113, D127, D141, D155	D169
Visit Window				± 1 days	± 2 days	± 2 days	± 2 days	± 2 days	± 2 days		± 2 days	± 2 days
Samples for anti-AZD8233 antibodies j			X	X		X		X		X	X j	X
Biomarker analyses (plasma) h	X		X	X	X	X	X	X	X	X	X	X
Biomarker analyses (urine) h			X	X	X	X	X	X	X	X	X	X
Genomics Initiative optional, exploratory genetic sample k			X									

Note: Participants are required to fast for at least 8 hours overnight prior to all study visits except for Visit 1; Participants are permitted to drink water during this period of fasting until 1 hour before blood sampling. On days where participants attend the clinic in a fasted state, blood and urine samples should be obtained prior to administration of IP.

Note: Samples to be obtained from all treatment arms unless specified in the table.

- a Home visits: may be undertaken at the participant's home or any other appropriate location by site staff or by qualified external service provider. Other visits currently not designated as 'home visits' may also be undertaken at the participant's home or any other appropriate location if deemed applicable, following consultation with the Investigator and the sponsor. Home visits performed by qualified external service provider (i.e. not by clinical trial site personnel) may only be performed starting Visit 5 (D22), excluding dosing visits (Visit 6 (D29) and Visit 8 (D57)).
- b Check screening labs and inclusion/exclusion criteria.
- c Weight should be measured in light indoor clothes, without shoes, after a prior visit to the bathroom.
- d Injection Site Reaction assessments to be collected based on adverse event collection criteria.
- e Vital signs and ECG to be measured pre-dose on dosing days.
- f ECG to be performed during the safety follow up period at Visits 10 (D85), 11 (D99), 13 (D127), and 15 (D155).
- g Blood samples for complement activation panel and coagulation parameters will be taken around Cmax and are to be collected pre-dose and 2 hours post-dose.
- h Samples to be obtained pre-dose on dosing days.
- i PK sampling to be performed at Visits 4 (D8), 6 (D29), 7 (D43), 8 (D57), 9 (D71), 10 (D85), 12 (D113) and 14 (D141) and final follow-up visit/EDV. Schedule of sampling for Visits 4 (D8), 6 (D29), 8 (D57) are shown below.
  - Visit 4 (Day 8; Loading dose): pre-dose
  - Visit 6 (Day 29; Dose 3): pre-dose
  - Visit 8 (Day 57; Final dose): pre-dose
- j ADA sampling to be performed at Visits 3 (D1), 4 (D8), 6 (D29), 8 (D57), 10 (D85), 12 (D113), and 14 (D141), and final follow-up visit/EDV. ADA samples to be collected pre-dose on all dosing days.
- k If, for any reason, the sample is not drawn pre-dose on Visit 3 (D1), it may be taken at any visit until the Final follow-up/EDV visit.
- l Visit 1 and visit 2 may be combined.

BMI = body mass index; CSP = clinical study protocol; D = day; ECG = electrocardiogram; EDV = early discontinuation visit; HbA1c = haemoglobin A1c; LDL-C = low-density lipoprotein cholesterol; PCSK9 = proprotein convertase subtilisin/kexin type 9; RTSM = Randomization and Trial Supply Management.

### 1.3 Number of subjects

Approximately 108 participants will be randomly assigned to study intervention such that at least 80 evaluable participants complete the study. Any participant who receives at least one dose of study intervention is considered evaluable and is included in the full analysis set. Participants are randomly assigned to study treatment in a ratio of 1:1:1:1.

The sample size of 20 participants per arm will provide 90% power in a two-sided t-test at 5% significance level to detect a difference of 0.33 on the logarithmic scale; 0.33 on the logarithmic scale is considered sufficient to distinguish the effect of the CCI dose from the effect of the CCI dose. The common SD for log-transformed LDL-C is assumed to be 0.3.

## 2 ANALYSIS SETS

### 2.1 Definition of analysis sets

All analysis sets are reported in the table below.

**Table 2 Populations for Analysis**

Population/Analysis set	Description
All enrolled subjects	All participants who sign the ICF.
All randomized subjects	All participants who were randomized. Participants will be analysed according to the treatment to which they were randomized.
Full analysis set	All randomized participants who received at least one dose of IP, in accordance with the intention to treat principle. Participants will be included in the analysis according to the treatment to which they were randomized. This is the primary analysis set.
Safety analysis set	All participants randomly assigned to study treatment and who take at least 1 dose of study treatment and for whom any post-dose data are available. Participants will be analysed according to the treatment which they actually received. If a participant received study intervention from the wrong kit for only part of the treatment duration and then switched to another, the associated treatment group for that participant will be the treatment group that participant was randomized to.
ADA analysis set	All participants randomly assigned to study treatment and who take at least 1 dose of study treatment and had at least one ADA assessment available. Participants will be included in the analysis according to the treatment to which they were randomized.
PK analysis set	All participants in the full analysis set who have at least one PK sample post dose. A patient will be considered as having at least one PK sample post dose if he has at least one plasma concentration that is not below LLOQ after the first dose. Subjects will be analysed according to the treatment which they actually received. However, only samples taken on patients planned to receive active

	treatment are analysed. Thus, patients planned to receive placebo but who finally received active treatment will not have any result available.
--	---

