## 6.3 Measures to Minimise Bias: Randomization and Blinding

All participants will be centrally assigned to randomized study intervention using a RTSM

system. Before the study is initiated, the telephone number and call-in directions and/or the log in information & directions for the RTSM will be provided to each site.

To simplify supply of study drug, randomization will be stratified based on the region in which the site is located. This will achieve greater balance within each region compared to simple randomization. Currently, two regions are planned: Europe and North America.

Study intervention will be dispensed at the study visits summarized in SoA.

The RTSM will provide to the Investigator(s) or pharmacists the kit identification number to be allocated to the participant at the dispensing visit. Routines for this will be described in the RTSM user manual that will be provided to each centre.

The randomisation code should not be broken except in medical emergencies when the appropriate management of the participant requires knowledge of the treatment randomisation. The Investigator documents and reports the action to AstraZeneca, without revealing the treatment given to participant to the AstraZeneca staff. AstraZeneca retains the right to break the code for SAEs that are unexpected and are suspected to be causally related to an investigational product and that potentially require expedited reporting to regulatory authorities. Randomisation codes will not be broken for the planned analyses of data until all decisions on the evaluability of the data from each individual participant have been made and documented.

The RTSM will be programmed with blind-breaking instructions. In case of an emergency, in which the knowledge of the specific blinded study treatment will affect the immediate management of the participant's condition (eg, antidote available), the Investigator has the sole responsibility for determining if unblinding of a participants' intervention assignment is warranted. Participant safety must always be the first consideration in making such a determination. If a participant's intervention assignment is unblinded, the sponsor must be notified within 24 hours after breaking the blind. The Investigator documents and reports the action to AstraZeneca, without revealing the treatment given to participant to the AstraZeneca staff.

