#### **8.5.1.1 Determination of Drug Concentration**

Samples for determination of drug concentration (AZD8233 full lengths ASOs) in plasma will be assayed at bioanalytical test sites operated by or on behalf of AstraZeneca, using an appropriately validated bioanalytical method. Full details of the analytical method used will be described in a separate bioanalytical report.

Placebo samples will not be analysed, unless there is a need to confirm that correct treatment has been given to study participants.

Drug concentration information that would unblind the study will not be reported to investigative sites or blinded personnel until the study has been unblinded.

Incurred sample reproducibility analysis or additional assay development/validation work, if any, will be performed alongside the bioanalysis of the test samples. The results from the evaluation, if performed, will be reported in a separate Bioanalytical Report.

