**Table 8 Populations for Analysis**

| Population/Analysis set       | Description   |
|--------------------------------------|--|
| Enrolled                             | All participants who sign the ICF.   |
| Randomly assigned to study treatment | All participants who were randomized. Participants will be analysed according to the treatment to which they were randomized.  |
| Full analysis set                    | All randomized participants who received at least 1 dose of study intervention, in accordance with the intention to treat principle. Participants will be included in the analysis according to the treatment to which they were randomized. This is the primary analysis set.   |
| Safety analysis set                  | All participants randomly assigned to study treatment and who take at least 1 dose of study treatment and for whom any post-dose data are available.

Participants will be analysed according to the treatment which they actually received. If a participant received study intervention from the wrong kit for only part of the treatment duration and then switched to another, the associated treatment group for that participant will be the treatment group that participant was randomized to. |
| PK analysis set                      | All participants who received at least one dose of study treatment and who had evaluable PK data.  |

Any important protocol deviations from randomized treatment will be listed and considered when interpreting the data. Important protocol deviations will be defined in the Non-compliance Handling Plan (NHP).

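### After a wrong kit, a placebo participant exposed to AZD8233 can be counted under placebo for safety and always is for ADA, and the SAP's PK sentence conflicts with the protocol

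*SAP*

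**What the plan says.** **Safety set.** The default in SAP Table 2 is "Participants will be analysed according to the treatment which they actually received", and Protocol Table 8 has the same default. Both then make one exception. The condition is "If a participant received study intervention from the wrong kit for only part of the treatment duration and then switched to another"; the consequence is that "the associated treatment group for that participant will be the treatment group that participant was randomized to".

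**ADA set.** This set is defined only in SAP Table 2. It takes dosed participants who "had at least one ADA assessment available. Participants will be included in the analysis according to the treatment to which they were randomized". It has no treatment-received rule.

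**PK set.** SAP Table 2 groups by treatment received, but then says that only samples from participants assigned to active drug are assayed, so that "patients planned to receive placebo but who finally received active treatment will not have any result available". Protocol 8.5.1.1 is less absolute: "Placebo samples will not be analysed, unless there is a need to confirm that correct treatment has been given to study participants".

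**Dispensing.** Under Protocol 6.3 the RTSM supplies "the kit identification number to be allocated to the participant at the dispensing visit". There are four dosing visits (Days 1, 8, 29 and 57), so a kit error confined to some of the doses is possible.

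**The concern.** A by-arm safety or immunogenicity table is read as drug against no drug. If a participant who received AZD8233 sits in the placebo column, an adverse event, platelet fall or treatment-emergent ADA caused by the drug raises the placebo rate and narrows the apparent difference. The exposure need not be short-lived. Protocol 4.2 gives an estimated terminal half-life of 2 to 3 weeks, and SAP Table 5 runs the on-treatment phase to the end of the study. Every later event in that participant would be tabulated under placebo.

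There are also two inconsistencies in the plan. The safety and ADA sets can put the same participant in different arms, with no explanation. And the SAP rules out a PK result in the one situation for which the protocol keeps the assay open.

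**Working it through.** The plan states no figure on this point, so there is none to reproduce. The check applies the written rules to each kind of kit error, then gives a scale.

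**Step 1. Where a placebo-randomised participant given AZD8233 would be counted.**

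| Kit error | Safety set | ADA set | PK result under SAP Table 2 |
|---|---|---|---|
| Wrong kit for one or more doses, then back to placebo | Placebo (exception) | Placebo | None |
| Wrong kit throughout | AZD8233 (default) | Placebo | None |
| Wrong first kit, then dosing stops | AZD8233 (default, as no switch occurred) | Placebo | None |
| Wrong kit at the last dose only | Unclear: no switch follows the wrong kit | Placebo | None |

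In the first row the two sets agree, and both say placebo. In the second and third rows they disagree. The overview of adverse events by ADA category (SAP 4.2.6.1) is run on the safety set, while ADA status is summarised on the ADA set (SAP 4.2.5.4). In those rows the same participant would appear under AZD8233 in one table and under placebo in the other.

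**Step 2. PK.** Entry to the PK set requires at least one quantifiable post-dose concentration. If samples are never assayed, the participant cannot enter the set, so grouping by treatment received cannot operate for anyone randomised to placebo. Under Protocol 8.5.1.1 the samples could be assayed to check treatment, and a quantifiable result would then bring the participant in. SAP section 6, which lists departures from the protocol, does not mention this one.

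**Step 3. Is any by-arm summary repeated by actual exposure?** Sensitivity analysis 1 (SAP 4.1.3) excludes participants given the wrong treatment, but it repeats only the log-normal MMRM, which is an efficacy model. SAP 4.2.5.4 and 4.2.6 contain no equivalent for ADA or safety.

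**Step 4. Scale.** Inputs from SAP 1.3: about 108 participants, 1:1:1:1.

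- Planned placebo arm: 108 / 4 = 27.
- One affected participant: 1/27 = 3.7 percentage points (0/27 becomes 1/27).
- Two: 2/27 = 7.4 points. Three: 3/27 = 11.1 points.
- With 20 per arm, the size used for the power statement: 1/20 = 5.0 points.

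The documents give no expected number of kit errors. One to three is an assumed range, and at zero the effect is nil.

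**The case against.** The case for leaving the plan alone has real weight.

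- The default for safety is treatment received, and protocol and SAP state the same exception. Mixed exposure needs some rule, and the randomised arm is a defensible, prespecified choice.
- Kit errors should be uncommon. Assignment is central through the RTSM, and for dosing at the site a second staff member confirms dose and identity (Protocol 6.4).
- An error can be traced. Randomisation code and actual kit are listed (SAP 4.2.1), important deviations are tabulated and listed (4.2.2), ADA results are listed with days since the previous dose (4.2.5.4), and adverse events and low or falling platelet counts are listed (4.2.6). Protocol 9.3 says that important deviations from randomised treatment will be considered in interpretation.
- Safety is descriptive, so no test is biased, and the primary LDL-C analysis is by randomised arm in any event.
- The SAP's PK sentence sits in an analysis-set definition; the protocol section governs the assay.

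Most of this stands, and it limits the weight of the point. It does not remove it. Listings leave the placebo column of the by-arm tables as it is, the different grouping of the ADA set is unexplained, and the PK conflict exists on paper whether or not an error occurs.

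**Conclusion.** The point holds and is minor. If a placebo participant receives AZD8233 for part of treatment and is then switched back, the written rule puts that participant in the placebo safety summaries. ADA results stay under placebo in every case. The SAP's PK sentence conflicts with Protocol 8.5.1.1 without being declared. The size is 3.7 percentage points of the placebo arm per affected participant, on the assumptions of 27 per arm and at least one kit error.

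Three stronger readings are tempting, and the documents do not support them:

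- A reader might infer that treatment received governs safety only if all four kits were wrong. The exception needs both partial exposure and a later switch, so a participant who stops after a wrong first kit stays under the default.
- A reader might infer that the safety and ADA tables conflict for every kit error. They conflict only where the default applies; after a partial error with a switch back they agree.
- A reader might infer that the samples could not be read at all. The protocol still permits the assay; it is the SAP wording that denies the result.

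**What to change.** 1. In the safety row of SAP Table 2 and Protocol Table 8, and in the ADA row of SAP Table 2, state that for these summaries the placebo group holds only participants who never received AZD8233. A placebo-randomised participant with any AZD8233 dose is counted as AZD8233-exposed or shown separately; choose one in advance. This also settles the wrong-last-kit case for placebo participants.
2. Give the ADA set the same treatment-received rule as the safety set.
3. Leave the existing rule for mix-ups between active doses unchanged. Assigning everyone to the highest dose received would move a participant with a single wrong kit into a higher-dose arm and could distort the dose comparison.
4. Reword the PK sentence so that samples from placebo participants with a documented wrong kit may be assayed, as Protocol 8.5.1.1 permits.

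The cost is wording in two tables and, if an error occurs, assay of a few samples before they are disposed of under Protocol 8.5. The downside is that adverse events that began before the misdirected dose may be counted under AZD8233; showing such participants separately avoids that.
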